6.2 Nonserious Adverse Events

A *nonserious adverse event* is an AE not classified as serious.

6.2.1 Nonserious Adverse Event Collection and Reporting

The collection of nonserious AE information should begin at initiation of study drug. Nonserious AE information should also be collected from the start of a placebo lead-in period or other observational period intended to establish a baseline status for the subjects.

Nonserious AEs should be followed to resolution or stabilization, or reported as SAEs if they become serious (see [Section 6.1.1](#)). Follow-up is also required for nonserious AEs that cause interruption or discontinuation of study drug and for those present at the end of study treatment as appropriate. All identified nonserious AEs must be recorded and described on the nonserious AE page of the CRF (paper or electronic).

Completion of supplemental CRFs may be requested for AEs and/or laboratory abnormalities that are reported/identified during the course of the study.

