3.6 Post Treatment Study Follow up

Subjects who discontinue study treatment will continue to be followed. The subjects will be followed up for select AEs beyond 100 days from the last dose of study therapy, for ongoing drug-related AEs until resolved, return to baseline or deemed irreversible, or until lost to follow-up or withdrawal of study consent.

One of the exploratory end points is overall survival and every attempt will be made to obtain survival status every 3 months until death, lost to follow-up, or withdrawal of study consent.

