Adverse Events Assessment	X	X	*Beyond 100 days from the last dose of study therapy, subjects will be followed for ongoing drug-related AEs until resolved, return to baseline or deemed irreversible, or until lost to follow-up or withdrawal of study consent.

Table 5.1-3: Follow-up Procedural Outline (CA209153)

Procedure	Initial Follow-Up Phase (100 days from the date of last study treatment) Follow-up Visit 1 (X01) and Visit 2 (X02)	Further Follow-up Phase (beyond X02)	Notes 
 • Subjects who discontinue treatment prior to randomization and subjects in Cohort A: Follow-up Visit 1 (X01) is to occur 30 days (\pm 5 days) after last dose or coinciding with the date of discontinuation (\pm 5 days) if date of discontinuation is greater than 35 days after last dose. • Subjects in Cohort B: Follow-up Visit 1 (X01) is to occur 30 days (\pm 5 days) after disease progression and a decision has been made to not retreat the subject or at 30 days (\pm 5 days) of discontinuation after retreatment • Follow up Visit 2 (X02) is to occur approximately 70 days (\pm 5 days) after X01
Laboratory Tests	X		CBC with differential, serum chemistry (BUN or serum urea level, serum creatinine, albumin, sodium, potassium, calcium, magnesium, phosphate, chloride, glucose), liver function (AST, ALT, total bilirubin, alkaline phosphatase, LDH), thyroid function (TSH, reflex to free T3 and free T4 if abnormal result)
Review of concomitant medications	X		
Pregnancy testing	X		
EQ-5D	X	X	Beyond 100 days from the last dose of study therapy, the EQ-5D will be administered every 3 months for the first 12 months, then every 6 months thereafter, as permitted by local IRB
Collection of Survival Information	X	X	Every 3 months until death, lost to follow-up, or withdrawal of study consent for 5 years following start of therapy. May be performed by phone contact or office visit.

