If an ongoing SAE changes in its intensity or relationship to study drug or if new information becomes available, a follow-up SAE report should be sent within 24 hours to the BMS (or designee) using the same procedure used for transmitting the initial SAE report.

All SAEs should be followed to resolution or stabilization.

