8.3.2 Secondary Endpoint(s)

The secondary objective of the study will be assessed by measuring the following:

- incidence for high grade (Grade 3-4 and Grade 5) select adverse events
- median time to onset, median time to resolution (Grade 3-4)
- percentage of subjects who received immune modulating medication (e.g. corticosteroids, infliximab, cyclophosphamide, IVIG, and mycophenolate mofetil), or hormonal replacement therapy, the percentage of subjects who received ≥ 40 mg prednisone equivalents, total duration of all immune modulating medications given for the select event.

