8.4.3 Secondary Analyses

The number and percentage of subjects who report high grade (Grade 3-4 and Grade 5) select adverse events will be summarized for all treated subjects. High grade (Grade 3-4 and Grade 5) select adverse events will be tabulated using worst grade per NCI CTCAE v4.0 criteria by system organ class and Medical Dictionary for Regulatory Affairs (MedDRA) preferred term.

Additional descriptive statistics will include median values using the Kaplan-Meier (KM) product-limit method with 95% CI using Brookmeyer and Crowley method of time to onset and time to resolution, and will be presented for all treated subjects, by tumor histology (SQ or NSQ), by subject subgroups, and all randomized subjects for Cohorts A and B. Time to onset is calculated from first dosing date to the event onset date. If a subject never experienced the given AE, the subject will be censored at the last contact date. Time to resolution is calculated from the

AE onset date to AE end date. If an AE is ongoing at the time of analysis, the time to resolution will be censored at the last contact date.

Management of high-grade (CTCAE v4.0 Grade 3-4 and Grade 5) select adverse events will be characterized by measuring percentage of subjects who received immune modulating medication (or hormonal replacement therapy), percentage of subjects who received ≥ 40 mg prednisone equivalents, and total duration of all immune modulating medications given for the event, in all treated subjects who have experienced high-grade (CTCAE v4.0 Grade 3-4 and Grade 5) select adverse events, by tumor histology (SQ or NSQ), and also by subject subgroups, and all randomized subjects in Cohorts A and B.

8.4.4 *Exploratory Analyses*

8.4.4.1 *Safety Analyses:*

All safety data will be summarized and listed for all treated subjects. All on-study AEs, SAEs, treatment-related AEs, and treatment-related SAEs will be summarized using worst grade per NCI CTCAE v4.0 by system organ class and preferred term. On-study lab abnormalities including hematology, chemistry, liver function, thyroid function, and renal function will be summarized using worst grade per NCI CTCAE v4.0 criteria.

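### AE follow-up may stop at an undefined stabilization, yet Section 8.4.3 keeps the unresolved event at risk to last contact, so the time-to-resolution estimate can depend on when sites stop looking

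*Combined protocol and SAP*

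**What the plan says.** The Combined protocol and SAP gives two sets of stopping points for following an AE.

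- **Sections 6.1.1 and 6.2.1.** For serious events: "All SAEs should be followed to resolution or stabilization". For nonserious events: "Nonserious AEs should be followed to resolution or stabilization, or reported as SAEs if they become serious". Both apply whatever the causality and carry no time window. Stabilization is not defined.
- **Section 3.6 and Table 5.1-3.** Beyond 100 days after the last dose, subjects are followed "for ongoing drug-related AEs until resolved, return to baseline or deemed irreversible, or until lost to follow-up or withdrawal of study consent". Stabilization is not in this list.

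On the analysis side, Section 8.3.2 names median time to resolution (Grade 3-4) as a secondary endpoint. The secondary objective in Section 1.3.2 covers all high-grade select AEs, not only drug-related ones. Section 8.4.3 measures from AE onset to AE end date and adds: "If an AE is ongoing at the time of analysis, the time to resolution will be censored at the last contact date". Table 5.1-3 provides for survival contact every 3 months, by phone if wished, for 5 years from the start of therapy.

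**The concern.** A site that reads Section 6 may close a plateaued event. A site that reads Section 3.6 may keep checking it. The documents do not say whether stabilization produces an AE end date. If it does not, the event is ongoing under Section 8.4.3 and stays in the risk set through later survival contacts, although its status is no longer being assessed. If a site does enter the stabilization date as the end date, an unresolved event is counted as resolved.

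Characterizing the outcome of these events is part of the secondary objective. It is also one of the reasons given for the sample size (Section 8.1) and for the 500 added subjects (Section 1.1.1). The estimate should not depend on site or data-entry habit.

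**Working it through.** **1. Where the rules meet.**

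| Event | Stopping rule in the text |
|---|---|
| Drug-related, up to 100 days after last dose | 6.1.1 / 6.2.1 only |
| Drug-related, ongoing beyond 100 days | Both sets, not reconciled |
| Judged unrelated | 6.1.1 / 6.2.1 only |

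Section 3.6 opens with select AEs in general, but it attaches end-states only to drug-related ones.

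**2. Figures in the plan.** The plan states no figure for time to resolution, so there is none to reproduce. Every input below is an assumption, except the survival range cited in step 5.

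**3. Size if closed events get no end date.** Let resolution be exponential with true median m. A share p of all events is closed at time c, chosen at random from those still unresolved, and censored at last contact. If last contact is independent of resolution, the large-sample Kaplan-Meier curve is unchanged up to c, and after that

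S(t) = p + (2^(-c/m) - p) × 2^(-(t-c)/m).

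The median is c - m × log2[(0.5 - p)/(2^(-c/m) - p)] if 2^(-c/m) > 0.5. Otherwise it stays at m.

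With m = 6 weeks and p = 20%:
- c = 0: -6 × log2(0.3/0.8) = 8.5 weeks
- c = 4: 2^(-4/6) = 0.630, so 4 - 6 × log2(0.3/0.430) = 7.1 weeks
- c = 6 or later: 6.0 weeks

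| Closure time (m = 6) | p = 10% | 20% | 30% |
|---|---|---|---|
| From onset | 7.0 | 8.5 | 10.8 |
| Week 4 | 6.4 | 7.1 | 8.3 |
| Week 6 or 8 | 6.0 | 6.0 | 6.0 |

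With m = 12 weeks and p = 20%, the median is 17.0 (closure from onset), 14.2 (week 8) or 12.0 (week 12).

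The late part of the curve moves even when the median does not. With full follow-up and m = 6, the proportion resolved by week 52 is 1 - 2^(-52/6) = 99.8%. With closure at week 6 it is 1 - [p + (0.5 - p) × 2^(-46/6)], which gives 90%, 80% and 70%. In simulation it is a few points lower if the closed share is drawn only from subjects still in contact at closure.

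**4. Direction.** A second illustration (200,000 simulated events per row) lets a share of events plateau at 12 weeks and resolve late, at a median of 40 weeks from onset. Last contact has a median of 40 weeks. Cells show the Kaplan-Meier median in weeks and the percentage resolved by week 52.

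| Median of other events | Share that plateaus | Followed to resolution | Stopped, no end date | Stabilization date entered as end date |
|---|---|---|---|---|
| 6 | 10-30% | 7.0-10.9; 96-89% | 7.0-10.9; 90-70% | 7.0-10.9; about 100% |
| 6 | 50% | 17.5; 81% | 47.7; 50% | 12.0; about 100% |
| 12 | 20% | 16.0; 89% | 17.1; 76% | 12.0; 96% |
| 12 | 40% | 21.0; 82% | 31.1; 57% | 12.0; 97% |

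**5. Does censoring at last assessment repair it?** I simulated the step 3 inputs with m = 6 and last contact at a median of 7.5 months, the middle of the 6.7 to 8.3 month historical survival range in Section 1.4.2. Censoring closed events at the closure date returned a median of 6.0 weeks and about 99.8% resolved by week 52, for closure from onset or at week 4, 6 or 8. This works because closure was unrelated to later resolution.

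**The case against.** **A general rule plus a stricter one.** A reader might infer that the two sets of rules contradict each other for every AE. The text does not support that. Sections 6.1.1 and 6.2.1 can be read as the general rule, with Section 3.6 and Table 5.1-3 adding a stricter one. They overlap only for drug-related AEs past day 100. This objection stands, but it leaves unrelated select AEs with only the undefined stop.

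**Status is checked anyway.** On treatment, AEs are assessed continuously (Table 5.1-2). Subjects with a delayed dose are re-evaluated at least weekly (Section 4.3.1.1), and resumption depends on AE status (Section 4.3.3). AE assessment is also scheduled at X01 and X02. This narrows the exposed set, mainly to select AEs judged unrelated after X02 and to drug-related AEs for which a site applies Section 6 instead of Section 3.6.

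**The shift may be nil.** A reader might take the largest shifts in step 3 as the expected bias, or express them as multiples of a standard error. The documents do not support either. Those shifts need closure at random from onset, whereas a stabilized event has by nature already lasted some time. Nor is lengthening certain, because the end date for a stabilized event is undefined.

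**Irreversible is also a stop without resolution.** This is true. Moving the Section 3.6 wording into Section 6 would not be enough without an analysis rule for unresolved end-states.

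**Low stakes.** The endpoint is descriptive. No test, alpha, power or primary incidence estimate is affected.

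**Conclusion.** The point holds as an unreconciled overlap in follow-up rules joined to a censoring gap, and the gap is the larger part. As written, Section 8.4.3 can count an AE as at risk and unresolved after its status was last assessed. This rests on reading last contact as including survival-only contacts, which nothing in the plan excludes.

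Size and direction are unknown. Under the 6-week assumption with 10-30% of events closed, the median shift runs from zero to about 5 weeks, and the proportion resolved by week 52 can fall from nearly 100% to about 70-90%. If stabilization dates are entered as end dates, the estimate can move the other way. The documents give neither the share closed nor its timing. The change is worth making because it is cheap and the endpoint is named, not because a large bias has been shown.

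**What to change.** 1. **Section 8.4.3.** Censor unresolved AEs at the last date AE status was assessed, not at last contact. Count only resolved or returned to baseline as the event. State that a stabilization date is not an end date, and keep AEs deemed irreversible as unresolved. Section 8.3.3 already works this way for PFS, which is censored at the last evaluable tumor assessment.
2. **Sections 6.1.1, 6.2.1, 3.6 and Table 5.1-3.** Reconcile them so that all high-grade select AEs share one set of follow-up end-states, with the end-state and its date recorded.

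The cost is wording, one outcome field and some status checks at contacts that already take place. For scale, 5% of 1280 is 64 subjects, using the Grade 3-4 treatment-related rate among the NSCLC subjects in MDX1106-03 (Section 1.1). Unrelated events would add to that. The statistical downside is that censoring at last assessment can be informative if stabilized AEs resolve more slowly than the rest. A sensitivity analysis that censors at last contact would show how much this matters.

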6.3 Laboratory Test Result Abnormalities

The following laboratory test result abnormalities should be captured on the nonserious AE CRF page or SAE Report Form (paper or electronic) as appropriate:

- Any laboratory test result that is clinically significant or meets the definition of an SAE
- Any laboratory test result abnormality that required the subject to have study drug discontinued or interrupted
- Any laboratory test result abnormality that required the subject to receive specific corrective therapy.

It is expected that wherever possible, the clinical rather than laboratory term would be used by the reporting investigator (eg, anemia versus low hemoglobin value).

6.4 Pregnancy

If, following initiation of the investigational product, it is subsequently discovered that a study subject is pregnant or may have been pregnant at the time of study exposure, including during at

least 5 half lives after product administration, the investigator must immediately notify the BMS (or designee) Medical Monitor of this event and complete and forward a Pregnancy Surveillance Form to BMS (or designee) within 24 hours and in accordance with the SAE reporting procedures described in [Section 6.1.1](#).

In most cases, the study drug will be permanently discontinued in an appropriate manner (eg, dose tapering if necessary for subject safety).

In the rare event that the benefit of continuing study drug is thought to outweigh the risk, after consultation with BMS, the pregnant subject may continue study drug, after a thorough discussion of benefits and risk with the subject.

Protocol required procedures for study discontinuation and follow-up must be performed on the subject unless contraindicated by pregnancy (eg, x-ray studies). Other appropriate pregnancy follow-up procedures should be considered if indicated.

Follow-up information regarding the course of the pregnancy, including perinatal and neonatal outcome and where applicable, offspring information must be reported on the Pregnancy Surveillance form

6.5 Overdose

An overdose is defined as the accidental or intentional administration of any dose of a product that is considered both excessive and medically important. All occurrences of overdose must be reported as an SAE (see Section 6.1.1 for reporting details.).

6.6 Potential Drug Induced Liver Injury (DILI)

Wherever possible, timely confirmation of initial liver-related laboratory abnormalities should occur prior to the reporting of a potential DILI event. All occurrences of potential DILIs, meeting the defined criteria, must be reported as SAEs (see Section 6.1.1 for reporting details).

Potential drug induced liver injury is defined as:

1. AT (ALT or AST) elevation > 3 times upper limit of normal (ULN)
AND
2. Total bilirubin > 2 times ULN, without initial findings of cholestasis (elevated serum alkaline phosphatase)
AND
3. No other immediately apparent possible causes of AT elevation and hyperbilirubinemia, including, but not limited to, viral hepatitis, pre-existing chronic or acute liver disease, or the administration of other drug(s) known to be hepatotoxic.

6.7 Other Safety Considerations

Any significant worsening noted during interim or final physical examinations, electrocardiogram, x-ray filming, any other potential safety assessment required or not required by protocol should also be recorded as a nonserious or serious AE, as appropriate, and reported accordingly.

For recommendations regarding suspected pulmonary toxicity, diarrhea and colitis, suspected hepatotoxicity (including asymptomatic LFT elevations), or suspected endocrinopathy, please see the Evaluation and Management Guidelines found in the Investigator Brochure.

7 DATA MONITORING COMMITTEE AND OTHER EXTERNAL COMMITTEES

The sponsor of this study will not utilize an independent data safety monitoring board (DSMB). BMS will assign a physician responsible for reviewing, on a systematic and continuous basis, the safety of subjects on this study. This includes a review of serious and non-serious adverse events, and all hematological and non-hematological events. In addition, BMS has a Medical Surveillance Team (MST), independent from the clinical medical monitor. The MST has the primary responsibility within Bristol-Myers Squibb for assessing emerging safety trends, identifying potential safety signals, notifying appropriate stakeholders of relevant findings, and implementing risk mitigation activities to ensure the safety of patients participating in BMS trials. The MST is also responsible for reviewing data from all sources including non-clinical studies and clinical trials, monitoring the progress of various nivolumab (BMS-936558) safety support activities, and recommending and implementing necessary changes to the safety plan and any other specific safety-related activities.

8 STATISTICAL CONSIDERATIONS

8.1 Sample Size Determination

In general, for nivolumab monotherapy, the safety profile to date is similar across tumor types, while select treatment related adverse events of high grade (Grade 3-4) are rather uncommon. Their overall incidence was 6% in a previous Phase 1 trial that tested nivolumab at doses between 0.1 mg/kg to 10 mg/kg in 306 subjects with different recurrent or refractory malignancies (MDX-03). The incidence observed for similar AEs 0% in NSCLC subjects (n=129) was 0% for skin and renal AEs, and endocrinopathies; 1% gastro-intestinal, hepatic and infusion reaction AEs, and 2% for pulmonary events.⁷

In order to further characterize the frequency and outcome of such apparently infrequent safety events, the current study will treat with nivolumab approximately 780 subjects who have advanced or metastatic NSCLC and have progressed during or after at least one prior systemic regimen. This sample size will allow for estimating an incidence rate of 0.5% (n=4 subjects with events) with a 95% CI (confidence interval) of (0.14%, 1.31%), or an incidence rate of 2% (n=16 subjects with events) with a 95% CI of (1.18%, 3.31%). Furthermore, the sample size will allow for enough events such that the outcome of these rare events can be characterized.

Estimated 95% confidence intervals for various event rates for an overall population of 780 subjects, and for different size subpopulation are described in [Table 8.1-1](#).

Table 8.1-1: Estimated Incidence Rates and 95% Confidence Intervals for the Overall Study Population and Subpopulations

Sample Size	Incidence Rate (%)	Lower 95% CI (%)	Upper 95% CI (%)
780	0.5	0.14	1.31
780	1.0	0.44	2.01
780	2.0	1.18	3.31
780	5.0	3.58	6.77
400	1.0	0.27	2.54
400	2.0	0.87	3.90
400	5.0	3.08	7.62
300	1.0	0.21	2.89
300	2.0	0.74	4.30
300	5.0	2.83	8.11
200	1.0	0.12	3.57
200	2.0	0.55	5.04
200	5.0	2.42	9.00
100	2.0	0.24	7.04
100	5.0	1.64	11.28
100	10.0	4.90	17.62

CI: confidence interval

SAS 9.2 was used to generate the 95% exact confidence intervals.

